5. C-reactive protein (CRP): Substance secreted by the liver. Routine blood test performed as part of standard clinical care to measure inflammation and assess disease activity in RA.
6. Musculoskeletal ultrasound (see below)

Chart review to obtain additional participant information:

- Demographics: Age, sex, race/ethnicity, BMI, smoking
- Medical History: RA disease duration, RF, CCP, current DMARDs, current glucocorticoid dose, current NSAID use, opioid use, number of previous biologics/JAKi
- Comorbidities: Presence of peripheral joint osteoarthritis, chronic back pain/back osteoarthritis, anxiety, depression, sleep apnea, fibromyalgia

Provider measures:

1. Pre-ultrasound assessment/treatment form:
 - Assessment of the patient's disease activity: providers will select whether they think the patient is in remission, low, moderate, or high disease activity (does not need to match the patient's CDAI score)
 - Confidence in the disease activity assessment (1-10) on a visual analog scale (VAS). A VAS tries to measure a characteristic or attitude that is believed to range across a continuum of values and cannot be easily directly measured.
 - Treatment recommendations: Providers will be asked whether their recommendation for treatment is as follows: no change, increase disease modifying anti-rheumatic drugs (DMARD) dose, or add/switch DMARD.
2. Post-ultrasound assessment/treatment form:
 - Same as the pre-ultrasound form but completed after ultrasound results are reviewed

Musculoskeletal ultrasound assessment

- Bilateral hands/wrists with gray-scale and power doppler (to be performed by the musculoskeletal ultrasound department or by an ultrasound certified rheumatologist within 3 weeks of visit 1. Synovitis in the metacarpophalangeal joint (MCPs), proximal interphalangeal joint (PIPs), and wrists will be graded as absent, mild, moderate, or severe according to the validated OMERACT scoring system. Images will be stored to allow a second reader to score images to assess inter-rater reliability.
 - OMERACT is the acronym for an international, informally organized network initiated in 1992 aimed at improving outcome measurement in rheumatology. Data driven recommendations are prepared and updated by expert working groups. Recommendations include core sets of measures for most of the major rheumatologic conditions
 - Patients in whom all measured joints have absent or mild synovitis will be considered to have low synovitis scores

CONFIDENTIAL

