5.2.2 Visit 2 (Ultrasound assessment)

1. Ultrasound scheduling:
 - After enrollment, the CRC will schedule musculoskeletal ultrasound with either a rheumatologist certified in MSK ultrasound or the Penn Division of Musculoskeletal Radiology (MSK Radiology).
2. During ultrasound visit:
 - If participants did not complete REDCap surveys during or after the clinic visit, then surveys can be done in person at the time of the ultrasound visit.
 - Ultrasound will be performed by trained staff.
3. After the ultrasound:
 - Synovitis will be graded according to the validated OMERACT scoring system.
 - All study visits are complete. Any study related patient questions can be answered by CRC.
 - Results of the ultrasound will be emailed to providers via encrypted email along with an interpretation based on OMERACT scoring and post-ultrasound assessment/treatment form (see 3.3 Study Measures)

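### The ultrasound grade behind the primary endpoint need not come from a masked, non-treating reader, which leaves mainly the Aim 1 subgroup comparisons open to reader expectation

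*Combined protocol and SAP*

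**What the plan says.** Section 3.3 has the scan "to be performed by the musculoskeletal ultrasound department or by an ultrasound certified rheumatologist within 3 weeks of visit 1". Section 5.2.2 has the coordinator book it with "either a rheumatologist certified in MSK ultrasound or the Penn Division of Musculoskeletal Radiology", and adds "Ultrasound will be performed by trained staff" and "Synovitis will be graded according to the validated OMERACT scoring system". The grader is not named in either place.

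Under section 3.3, synovitis in the MCP joints, PIP joints and wrists "will be graded as absent, mild, moderate, or severe according to the validated OMERACT scoring system". The endpoint rule follows: "Patients in whom all measured joints have absent or mild synovitis will be considered to have low synovitis scores".

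The one relevant safeguard is also in 3.3: "Images will be stored to allow a second reader to score images to assess inter-rater reliability". The plan does not say whether that reader is masked, how many patients are re-read, or whether the second grade affects the endpoint.

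Section 6.3, on control of bias and confounding, deals only with the absence of confounding adjustment.

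**The concern.** The rationale for the study (sections 1 and 1.1) is that composite scores are distorted by factors such as fibromyalgia, depression and obesity, and that ultrasound may be a less biased measure. That advantage weakens if the person grading the images knows the same factors.

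Sections 3.4.1 and 6.3.2 compare the low-synovitis proportion across CRP, serostatus, biologic treatment, PSD, depression, and DAS28 and CDAI category. A reader who knows that a patient has a normal CRP or a fibromyalgia diagnosis may settle a borderline mild/moderate call accordingly. Part of the association later reported would then come from the reader. These comparisons are meant to shape the entry criteria of the next trial, so the error would carry forward.

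**Working it through.** **Step 1. What the text permits.**

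| Question | Section 3.3 | Section 5.2.2 | Section 6.3 |
|---|---|---|---|
| Who scans? | Ultrasound department or certified rheumatologist | MSK Radiology or certified rheumatologist; trained staff | – |
| Who grades? | Not named | Not named | – |
| Masked to clinical data? | Not stated | Not stated | Not stated |
| Treating provider excluded? | No | No | No |

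CDAI is done by the treating physician, CRP is routine care, and serology and comorbidities are in the chart (all section 3.3). A rheumatologist with chart access could know them. PSD and PROMIS are research surveys; 5.2.2 allows them to be completed at the ultrasound visit, but nothing says the grader sees the scores.

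**Step 2. How one joint call affects a patient's class.** The rates e below are assumptions, and joints are taken as independent.

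- *Upgrading.* A truly low patient with k mild joints, each called moderate with probability e, leaves the low class with probability 1 − (1 − e)^k.
- *Downgrading.* A truly not-low patient with m moderate or severe joints, each called mild with probability e, enters the low class only if all m are downgraded: e^m.

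| e | Up, k=1 | Up, k=3 | Up, k=5 | Down, m=1 | Down, m=2 |
|---|---|---|---|---|---|
| 1% | 1.0% | 3.0% | 4.9% | 1% | 0.01% |
| 5% | 5.0% | 14.3% | 22.6% | 5% | 0.25% |
| 10% | 10.0% | 27.1% | 41.0% | 10% | 1% |

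The rule magnifies upgrading and damps downgrading. Since e, k and m are not in the documents, none of these values is an estimate for this study.

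**Step 3. Effect on the primary proportion.** Section 4.2 expects about 40 consented and 20 evaluable; the synopsis gives 40 subjects. One reclassified patient moves the proportion by 1/20 = 5 points or 1/40 = 2.5 points. Suppose the true proportion is 50%:

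- If 10% or 20% of not-low patients are called low, it reads 0.5 + 0.5 × 0.1 = 55% or 0.5 + 0.5 × 0.2 = 60%.
- If 10% or 20% of low patients are called not low, it reads 0.5 × 0.9 = 45% or 0.5 × 0.8 = 40%.

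The exact (Clopper-Pearson) 95% interval at an observed 50% is 27.2–72.8% for n = 20 and 33.8–66.2% for n = 40. Shifts of this size lie inside it, so the data would not reveal them.

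**Step 4. Effect on a subgroup comparison.** Assume a true 50% low in both of two equal subgroups, a reader who calls a fraction f of the not-low patients low in one subgroup only, and a two-sided Fisher test at 0.05 (the plan states no level). That subgroup then reads 0.5 + 0.5f.

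| f | Apparent proportions | Test rejects, 10 vs 10 | Test rejects, 20 vs 20 |
|---|---|---|---|
| 0 | 50% vs 50% | 1.3% | 2.0% |
| 0.2 | 60% vs 50% | 2.2% | 4.9% |
| 0.4 | 70% vs 50% | 5.5% | 16.3% |

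At these sample sizes the main harm is a false apparent difference of 10 or 20 points; a significant p-value remains uncommon.

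**The case against.** The strongest reply is that the plan permits the problem but does not describe it. Results are emailed to the provider after the scan (5.2.2), which suggests that operator and provider are usually different people. The scale is validated, images are stored and a second reader is foreseen. The study is a descriptive pilot sized on feasibility and cost (6.1, 6.2), and sampling error is wide anyway. All of this is fair, and it limits the point to a gap in the safeguards. It does not close the gap: a validated scale still needs a reader's judgement, and two unmasked readers can agree while sharing one expectation. Wide sampling error is reported with an interval, whereas reading bias is not.

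Three stronger readings do not hold.

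- *That the bias runs toward low synovitis.* The rationale and the low swollen joint count pull that way, but a CDAI above 10 could push grades up. The objective is to determine a frequency, with no predicted value.
- *That small shifts compound over about 20 joints* (10 MCP + 8 PIP + 2 wrists, a count inferred from the named sites), so that a 1% shift misclassifies 1 − 0.99^20 = 18% of patients and a 2% shift 1 − 0.98^20 = 33%. That formula covers only upgrading in truly low patients and puts every joint at equal risk, although an absent joint would have to move two grades. For downgrading, e^m applies, and it shrinks as m grows.
- *That Aim 2 is invalid if the treating provider scans.* One person would then produce the result and react to it, which is undesirable. But the post-ultrasound form is meant to be completed with the results known, so this carries limited weight.

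**Conclusion.** The point holds as an unprotected endpoint assessment. Following the plan as written, an unmasked reader, not excluded from being the treating provider, can make the mild/moderate calls that set the primary endpoint. Some of the factors then tested against that endpoint may be known to the reader.

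The risk is clearest for the Aim 1 subgroup comparisons. For the primary proportion, bias is possible but its direction is unsettled. Its size cannot be derived for either, and the figures above only show how the rule and the sample size behave under assumed rates. A reader might infer that treating rheumatologists will grade their own patients; the documents only fail to exclude it.

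The change should be made because it is inexpensive and the results feed the next trial's design. The gap does not invalidate a descriptive pilot.

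**What to change.** In sections 3.3 and 5.2.2, state that the grade used for Aim 1 is made by someone other than the patient's treating provider, masked to that patient's individual CDAI, joint counts, laboratory results and survey scores. Either of two routes would do:

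1. The coordinator schedules a non-treating operator, who grades without access to those data.
2. The second read already foreseen is done on stored images labelled with subject ID only, and that grade is used for Aim 1.

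The provider continues to receive the routine report. Name the grader, and say which grade counts when two exist.

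Costs and limits:

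- Treating rheumatologists can no longer supply the endpoint grade for their own patients.
- Under the second route, the read must cover every evaluable patient (about 20 to 40); section 3.3 commits only to storing images so that a second read is possible.
- Aim 1 may then rest on a different grade from the one the provider saw in Aim 2, and the report should say so.
- Any reader who knows the protocol knows that every patient has CDAI above 10 and at most two swollen joints, so masking cannot hide eligibility. Re-reading stored images cannot undo bias in how they were acquired.

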3.3 Study Measures

Patient measures:

1. Routine Assessment of Patient Index Data (RAPID3): A pooled index of the 3 patient reported American College of Rheumatology (ACR) RA core data set measures: function, pain, and patient global estimate of status. Each of the 3 individual measures is scored 0 to 10, for a total of 30, and remission was defined as RAPID3 score ≤ 3 . All patients in Penn's rheumatology practice are currently asked to complete the RAPID3 prior to the visit as part of routine patient care. The RAPID3 survey will be used to identify patients more likely to be eligible for the study.
2. Clinical Disease Activity (CDAI): The CDAI is performed by the treating physician at the time of the clinic visit as part of routine care. CDAI is calculated as the sum of swollen joint count (SJC, 0-28), tender joint count (TJC, 0-28), patient global assessment (PGA, 0-10), evaluator global disease activity (EGA, 0-10). Tenderness and swelling are evaluated in the first through fifth metacarpophalangeal joint, the interphalangeal joint of the thumb, the second through fifth proximal interphalangeal joint, the wrists, elbows, shoulders, and knees. The PGA estimate represents the patient's self-assessment of disease activity on a 0-10 scale where 10 means maximal activity. The EGA estimate represents the evaluator's assessment of disease activity on a 0-10 scale where 10 means maximal activity.

CDAI ≤ 2.8 : Remission
CDAI > 2.8 and ≤ 10 : Low Disease Activity
CDAI > 10 and ≤ 22 : Moderate Disease Activity
CDAI > 22 : High Disease Activity

Provider must indicate CDAI >10 and SJC ≤ 2 and no large joint involvement for participant to be eligible.

3. Polysymptomatic Distress Questionnaire (PSD): Combined Widespread Pain Index (WPI), or measure of pain severity extent (0-19 scale) and Symptom Severity scale (SS), or measure of symptom severity (0-12 scale). The PSD scale, 0-31, is an overall

CONFIDENTIAL

This material is the property of the University of Pennsylvania.

measure of pain extent and symptom distress. Used as a diagnostic tool for fibromyalgia by the guidelines set by the 2010 ACR criteria.

4. PROMIS depression, pain, fatigue: Patient-Reported Outcomes Measurement Information System (PROMIS) is a set of person-centered measures that evaluates and can monitor physical, mental, and social health in individuals living with chronic conditions. Short form versions of these measures will be used.

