3.4 Study Endpoints

3.4.1 Primary Study Endpoint

The proportion of included patients with low synovitis scores will be calculated. Additionally, the proportion of patients with low-synovitis scores among those with disease activity score in 28 joints (DAS28 >3.2) will be evaluated. To assess patient characteristics associated with having low synovitis scores to inform inclusion criteria for a future interventional study, Fisher's exact tests will be used to compare the proportion of low synovitis scores in patients in certain prespecified subgroups:

- patients with long-standing versus earlier RA (>5 years vs ≤5 years)
- biologic vs. non-biologic treated patients, high versus low CRP (>1mg/dL vs. ≤1mg/dL)
- patients with vs. without evidence of central pain sensitization (PSD ≥12 vs <12)
- seropositive vs. seronegative
- patients with depression vs. those without (based on PROMIS vs. PHQ-9)
- moderate vs high disease activity by DAS28 and moderate vs high disease activity by CDAI
- associations with age, comorbidities, CDAI, DAS28, will also be assessed.

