5.1 Pre-screening/Screening

Patients with scheduled visits in the rheumatology clinic will be pre-screened for age, RA diagnosis, and DMARD treatment. If patients who are being pre-screened have already completed the RAPID3 survey, the survey score will be assessed for eligibility.

Patients will be contacted through the My Penn Medicine patient portal to inform them about the study and to remind them to complete their RAPID3 survey (sent to all patients in the practice as part of routine care), with the option to opt-out of further pre-screening assessments. Patients without My Penn Medicine or who do not complete the RAPID3 survey will be contacted by phone to inform them about the study and to administer the RAPID3 survey if patients are interested in the study. Patients may still be recruited on the day of their clinic visit, even if a RAPID3 has not been measured or is low, if the patient meets inclusion criteria on the day of the clinic visit.

RAPID3 eligibility criteria:

If RAPID3 ≤ 6 :

- Patients will be informed through MPM and/or phone that they are not likely eligible for the study at this time but might be at a future visit. Providers can still refer these patients to the study and they can be included if they meet inclusion criteria on the day of their office visit.

If RAPID3 > 6 :

- Patients will be informed through MPM and/or phone that they may be eligible for the study depending on their routine exam in clinic.
- Providers will be notified of potentially eligible patients

Providers will perform routine standard of care assessment of disease activity using the CDAI (see 3.3 Study Measures) at the patient's clinic visit. If the score meets the study eligibility criteria, the patient will be approached either at the clinic visit or by phone and asked if they are interested in the study. If they are, the consent process will be conducted.

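### Treatment given between the qualifying CDAI examination and the ultrasound is not a defined data item, so the low-synovitis proportion may be overstated by an unknown amount

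*Combined protocol and SAP*

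**What the plan says.** **Eligibility.** Section 3.3 states: "The CDAI is performed by the treating physician at the time of the clinic visit as part of routine care". The provider must find CDAI above 10, at most two swollen joints, and "no large joint involvement for participant to be eligible".

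**Timing of the scan.** The ultrasound is Visit 2 (section 5.2.2). Section 3.3 has it done by the musculoskeletal ultrasound department or "by an ultrasound certified rheumatologist within 3 weeks of visit 1".

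**Start of the window.** Visit 1 (section 5.2.1) consists of consent, patient surveys and the provider's pre-ultrasound form. Under section 5.1, once the CDAI qualifies, "the patient will be approached either at the clinic visit or by phone". Section 5.2.1 also allows consent by phone with an electronic signature.

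**Endpoint.** Section 3.3: "Patients in whom all measured joints have absent or mild synovitis will be considered to have low synovitis scores". Section 3.4.1: "The proportion of included patients with low synovitis scores will be calculated". Section 6.3.2 repeats this, and section 6.3 rules out adjustment for confounding.

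**Treatment data.** Chart review takes "current DMARDs, current glucocorticoid dose, current NSAID use", with no reference date. The pre-ultrasound form asks for a recommendation with three options: leave treatment as it is, raise a DMARD dose, or add or switch a DMARD. It has no glucocorticoid option. Section 5.2.2 asks nothing about treatment since the clinic visit and does not repeat the joint counts. The exclusion criteria (section 4.4) do not mention recent or interim treatment changes.

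**The concern.** The study asks how often an elevated CDAI goes with little synovitis. For that, score and scan should describe the same disease state, but here they are taken at different times. Every participant enters with a score that, by the protocol's own background (section 1.1), guidelines treat as a reason to escalate DMARD therapy. Nothing says that treatment waits for the scan.

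Two kinds of patient therefore end up in the same cell. In one, the CDAI was high without synovitis, which is the group the study wants to count. In the other, synovitis was present at the examination, was treated, and had settled by the scan. The planned data cannot reliably separate them.

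The result is meant to help choose entry criteria for a later intervention study. Sampling error shows in a confidence interval and shrinks in a larger study. A misclassification of this kind does neither, and without dated treatment information it is hard to reconstruct afterwards.

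**Working it through.** The plan states no expected proportion, power or error rate (section 6.1 bases the sample size on feasibility and cost), so there is no figure to reproduce. The check is a sensitivity model.

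**Inputs from the documents.** Section 4.2 expects about 40 consented and 20 evaluable patients. One patient is 1/20 = 5 points, or 1/40 = 2.5 points.

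**Assumed inputs (none is in the documents).**
- p0: true low-synovitis proportion at the examination, 0.3 to 0.7
- t: share of not-low patients whose treatment changes before the scan, 0.10 to 0.50
- e: share of those who have become low by the scan, 0.10 to 0.50
- f: share of truly low patients who worsen before the scan

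**Step 1: upward shift with no worsening.** Shift = (1 − p0) × t × e.

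| Case | p0 | t | e | Shift |
|---|---|---|---|---|
| Smallest | 0.7 | 0.10 | 0.10 | 0.3 × 0.01 = 0.003 (0.3 points) |
| Middle | 0.5 | 0.25 | 0.25 | 0.5 × 0.0625 = 0.03125 (3.1 points) |
| Largest | 0.3 | 0.50 | 0.50 | 0.7 × 0.25 = 0.175 (17.5 points) |

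In the middle case this is 0.03125 × 20 = 0.6 of 20 patients, or 0.03125 × 40 = 1.25 of 40. If t or e is zero, the shift is zero.

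**Step 2: worsening in the gap.** Net shift = (1 − p0) × t × e − p0 × f. In the middle case it is zero when f = 0.03125 / 0.5 = 6.25%. A larger f reverses the sign.

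**Step 3: sampling error.** Exact (Clopper-Pearson) 95% intervals at an observed 50%:
- 20 patients: 27.2% to 72.8%, half-width 22.8 points
- 40 patients: 33.8% to 66.2%, half-width 16.2 points

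At an observed 30% or 70% the half-widths are 21.2 points (20 patients) and 15.0 points (40 patients). With p0 at 0.3, 0.5 or 0.7, and t and e each at 0.10, 0.25 or 0.50, every shift is below the half-width for 20 patients. For 40, only the largest, 17.5 points, exceeds it.

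**Step 4: would restriction to unchanged patients correct it?** Assume p0 = 0.5, with treatment changed in 50% of not-low and 20% of low patients.
- Low and unchanged: 0.5 × 0.8 = 0.40. Not low and unchanged: 0.5 × 0.5 = 0.25.
- Restricted proportion, if treatment has no effect on synovitis: 0.40 / 0.65 = 61.5%, against a true 50%.
- All-scanned proportion: 50% with no effect, 0.5 + 0.5 × 0.5 × 0.25 = 56.3% with 25% conversion, 0.5 + 0.5 × 0.5 × 0.5 = 62.5% with 50% conversion.

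So restriction can add 11.5 points where there was no bias to remove.

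**Step 5: a bound instead.** Count low-synovitis patients with an interim anti-inflammatory start or increase as not low. If all the changes in Step 4 are of that kind, this gives 0.40 whatever the conversion rate. The true 50% then lies between 40% and the all-scanned value in all three cases. The bracket addresses interim treatment only. Spontaneous change, in particular worsening, is outside it.

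**The case against.** The strongest reply is that this is a feasibility pilot with a descriptive aim (sections 6.1 and 6.2), that a short scheduling window is ordinary practice, and that the plausible error is mostly smaller than the sampling error. That is fair. It limits how much weight the point carries, but does not remove it, because the remedy is cheap and the information is hard to recover later.

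Three stronger readings are tempting, and the documents do not support them.

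- *No treatment is recorded.* Current DMARDs, glucocorticoid dose and NSAID use are collected, as is the pre-scan recommendation. Low synovitis could be tabulated by that recommendation with no new fields. This is only a partial check: the drug data are undated, and a recommendation is not treatment given.
- *The proportion is biased upward.* The documents give no rate of interim treatment and none for synovitis settling before the scan. Worsening in the gap pushes the estimate down. An overstatement is a risk, not a demonstrated fact.
- *The gap exceeds 3 weeks.* Section 4.1 describes surveys after a routine visit plus one ultrasound visit, about a month in all. That is compatible with Visit 1 being the clinic visit and phone consent being a matter of logistics. A longer gap is possible under sections 5.1 and 5.2.1, but is not established.

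The objection to a restricted analysis also stands, as Step 4 of the working shows. If inflamed patients are treated more often, dropping them selects for low synovitis.

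**Conclusion.** The point holds as a gap in data capture. The qualifying examination and the endpoint scan are separated in time, the window is not explicitly tied to the examination, and treatment given in between is neither a defined data item nor part of any planned analysis. The primary proportion may therefore be overstated by an unknown amount.

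The range of 0.3 to 17.5 points, with 3.1 in the middle case, rests entirely on assumed rates and leaves out worsening. It shows what could happen and does not estimate what will. In the middle case the shift is less than one patient in 20. The change is worth making because it costs little and lets the study put limits on its main result.

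**What to change.** 1. **Sections 3.3 and 5.2.2:** count the 3-week window from the date of the qualifying CDAI and swollen joint examination.
2. **Section 5.2.2:** at Visit 2, record the examination date, the scan date, and any glucocorticoid (by any route), DMARD or NSAID started, stopped or changed between them.
3. **Sections 3.4.1 and 6.3.2:** keep the proportion in all scanned patients as primary. Tabulate low synovitis by interim change (yes or no). Add one sensitivity bound that counts low-synovitis patients with an interim anti-inflammatory start or increase as not low. State that this bound does not cover spontaneous change.
4. Do not present the proportion restricted to patients without a change as a corrected estimate.

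The analysis stays descriptive and consistent with section 6.3. The cost is a few REDCap fields at an existing visit, slightly tighter scheduling for patients who consent by phone, and one extra table line. No change to patient care is proposed.
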